### 4.3. Planned Interim Analyses

There are 3 planned interim reviews of PK data. The first interim review will occur after a minimum of 4 patients on LY3002813 in Cohort 2 complete Visit 10 (Day 29). The second interim PK data review is planned to occur after a minimum of 4 patients on LY3002813 in Cohort 3 (40 mg/kg IV single dose) complete Visit 8 (Day 85). The third interim PK data review is planned to occur after a minimum of 4 patients on LY3002813 in Cohort 4 and also in Cohort 5 (for a total of 8 patients) have completed Visit 16 (Day 141). Additional interim PK data reviews may also be conducted to summarize data for internal decision making and/or supporting subsequent clinical studies/regulatory agency/Investigator's Brochure (IB) annual updates, as required.

There are 2 planned interim reviews of AEs, clinical laboratory data, vital signs and imaging SUVR data. All available ADA titers will be included. These two planned interim review require study data tabulation model (SDTM) datasets for all safety data, ADA titer data and the amyloid

imaging SUVR values along with all available cognitive measurements. Descriptive summaries of all safety, ADA, PD imaging and cognitive measures will be computed by each IV dose group and placebo. Given the small sample sizes, more advance statistical evaluations will be conducted if appropriate.

1. The first review will occur after a minimum of 4 patients on LY3002813 in Cohort 3 (40 mg/kg IV single dose) complete Visit 13 (Day 169).
2. The second interim data review is planned to occur after a minimum of 4 patients on LY3002813 in Cohort 4 and also in Cohort 5 (for a total of 8 patients) have completed Visit 18 (Day 169). The second interim data review should coincide with the third PK data review. Associations between drug exposure and safety data, ADA titers and PD imaging SUVR will be assessed using simple graphical and pair-wise correlations.

As PD data accrues, there will be periodic reviews of PD data by the Lilly study team. Notably PD reviews will occur after a minimum of 4 patients on LY3002813 complete each scheduled florbetapir scan within each cohort.

In addition, safety will be reviewed by the Lilly study team on an ongoing basis. Safety review meetings will be conducted regularly with investigators.

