Study Design: This is a 3-part, patient- and investigator-blind, randomized within cohort, placebo-controlled, parallel-group, single- and multiple-dose study in patients with MCI due to AD or mild to moderate AD to assess the safety, tolerability, PK, and PD of single and multiple IV doses of LY3002813. The study will be conducted in at least 7 cohorts. 
 Cohort 1: 10 mg/kg IV single dose Cohort 2: 20 mg/kg IV single dose Cohort 3: 40 mg/kg IV single dose Cohort 4: 10 mg/kg IV Q2W for 24 weeks Cohort 5: 20 mg/kg IV Q2W for 24 weeks Cohort 6: 10 mg/kg IV Q4W for up to 72 weeks Cohort 7: 20 mg/kg IV Q4W for up to 72 weeks 	

Each cohort will contain approximately 6 (single dose) or 9 (multiple dose) patients treated with LY3002813 and 2 to 3 patients treated with placebo so that the study can detect target engagement and antidrug antibody (ADA) frequency relative to those observed in Study I5T-MC-AACC.

Diagnosis and Main Criteria for Inclusion and Exclusion:

The study will enroll men or nonfertile women, at least 50 years of age with evidence of memory impairment on the Free and Cued Selective Reminding Test with Immediate Recall (FCSRT-IR), a Mini-Mental State Examination (MMSE) 16 to 30, a Clinical Dementia Rating of 0.5 to 2 and memory box score ≥ 0.5 , no history of macrohemorrhage and no more than 4 microhemorrhages on MRI, and a positive amyloid scan by florbetapir. Patients with contraindication for MRI, presence of >4 microhemorrhages on MRI, or history or evidence on MRI of macrohemorrhage will be excluded. Criteria for Japanese patients: Japanese if recruited at sites in Japan or up to third-generation Japanese if recruited at sites outside of Japan. “Third-generation Japanese” is defined as a patient whose biological grandparents are of exclusive Japanese descent and were born in Japan.

Investigational Product, Dosage, and Mode of Administration:

LY3002813, single and multiple doses, from 10 mg/kg up to 40 mg/kg, IV infusion

Comparator, Dose, and Mode of Administration:

Placebo (saline), IV infusion

Planned Duration of Treatment:

Part A (Cohorts 1, 2, and 3): single dose of LY3002813 or placebo followed by 72 weeks (for Cohorts 1 and 2) and 24 weeks (for Cohort 3) follow-up for each dose level

Part B (Cohorts 4 and 5): 13 doses of LY3002813 or placebo administered Q2W for 24 weeks followed by 48-weeks follow-up

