5.2. Rationale and Justification for the Study

This is the second study with LY3002813 in patients with MCI due to AD or mild to moderate AD. Data from Study AACC indicated a dramatic reduction in cerebral amyloid (as assessed by florbetapir PET imaging) in the 6 patients who received 3 to 5 doses of 10 mg/kg of LY3002813 IV over 6 months, without cerebral vasogenic edema or microhemorrhage complications in this dose group. These positive results were accompanied by a high incidence of ADAs at all doses, as well as infusion reactions noted at doses ≤ 3 mg/kg. Dosing was stopped in the multiple-dose phase of Phase 1 Study I5T-MC-AACC (Study AACC) due to high prevalence of ADAs and unexpected rapid clearance of the study drug.

As a result of the significant target engagement (amyloid reduction by florbetapir PET) that was identified after 3 to 5 doses of LY3002813 10 mg/kg IV over 6 months, the current study is proposed to determine whether different dosing regimens (single-dose, short-term “induction” dosing with higher, more frequent dosing; and chronic dosing for maximal PD effect) can mitigate immunogenicity and immune safety issues, and produce sustained amyloid reduction. The aims of the study are to evaluate the effect of different dosing regimens on ADAs and amyloid plaque removal, and assess the relationship between PK, PD (amyloid removal), immunogenicity, and clinical safety. As a high prevalence of ADAs was observed in Study AACC, a risk management plan for immune safety will be incorporated into the clinical trial including at least 6 hours monitoring after completion of each infusion, a protocol for management of infusion reactions, and standardized data collection for infusion reaction AEs.

A favorable risk/benefit profile and dosing selection will support further development of LY3002813, including: (1) removal of amyloid consistent with Study AACC; (2) persistence of amyloid removal after completion of dosing; (3) acceptable clinical impact of ADAs; (4) manageable risk of clinically significant infusion reactions; and (5) low incidence of amyloid-related imaging abnormalities-edema (ARIA-E) and ARIA-H.

6. Objectives

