Multiple doses of 10 mg/kg IV were safe and tolerated in Study AACC. Clinical doses of 20 mg/kg and 40 mg/kg are 5- and 2.5-fold lower than the highest dose tested in monkeys (100 mg/kg/week), which was a no-observed-effect level. The ability to project human exposures at doses above 10 mg/kg is questionable, as the exposure at 10 mg/kg did not appear to be proportional with the exposures seen at lower doses. The clearance of LY3002813 appeared to be decreasing, and the half-life increasing, at the 10 mg/kg dose level relative to what was observed at lower doses. It is unclear whether this trend will continue at higher doses. Accordingly, in estimating the exposures that may be encountered at doses greater than 10 mg/kg, the clearance predicted based on nonclinical data (11.3 mL/h) was used, which is much more conservative than the clearance observed to date clinically (26.3 mL/h at the 10 mg/kg dose level). These exposure projections suggest that a dose of 40 mg/kg may result in exposure that exceeds that which was achieved at the no-observed-effect level in the 6-week monkey study ([Table AACD.3](#)). However, the monkey is an “off-target” species (does not possess deposited N3pG A β); further, the animal data did not predict the human findings with respect to PK or immunogenicity.

Table AACD.3. Margin of Safety for Intravenous Administration of LY3002813 Based on Administered (QW) Dose and Measured or Predicted Exposure

	Dose (mg/kg)	Dose Multiple ^a	AUC(0-168hr) (µg·hr/mL)	Exposure Multiple (AUC[0-∞]) ^a
Human ^b	0.1	1000	199	715
	10	10	27000	5.3
	20	5	124000	1.1
	40	2.5	248000	0.6
Monkey NOEL ^c	100	--	142219	--

Abbreviations: AACC = I5T-MC-AACC; AUC = area under the concentration-time curve; AUC(0-∞) = area under the concentration versus time curve from time 0 to infinite time; FDA = Food and Drug Administration; IV = intravenous; MW = molecular weight; NOEL = no-observed-effect level; QW = every week.

^a Dose multiple is the dose in animals/dose in humans based on mg/kg. For biological products administered IV with an MW >100,000 Da, scaling doses on a mg/kg basis is the preferred approach (FDA guidance for industry: estimating the maximum safe starting dose in initial clinical trials for therapeutics in adult healthy volunteers; Rockville, Maryland, United States FDA 2005).

Exposure multiple is the AUC in animals/AUC in humans (Study AACC interim data).

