#### 4.2.7.3. Evaluation of Immunogenicity (for Large Molecules)

As part of the secondary study objective, Antibody drug formation will be summarized over time for each IV dose group. An MMRM will be done fitting IV dose, study visit, and interaction between study visit and dose as fixed effects and the dependent variable as the change from baseline in antibody formulation following dosing of LY3002813. The relationship between the presence, absence or level of ADAs and number of IV drug infusion reaction AEs, PK estimates of exposure, PD measurements of amyloid SUVR. These associations may be assessed using simple pairwise correlations and pairwise graphical relationship. These relationships may also be described using a modeling approach, if appropriate.

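### ADA is to be related to exposure and to SUVr by simple pairwise correlations with no regimen term, so a correlation pooled over regimens would mix regimen differences with any ADA effect.

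*SAP*

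**What the plan says.** SAP 4.3, on the second interim safety and imaging review: "Associations between drug exposure and safety data, ADA titers and PD imaging SUVR will be assessed using simple graphical and pair-wise correlations". I read this as drug exposure paired in turn with safety data, ADA titre and SUVr. The same section adds "Given the small sample sizes, more advance statistical evaluations will be conducted if appropriate".

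SAP 4.2.7.3 lists ADA against infusion-reaction AEs, PK estimates of exposure and amyloid SUVr, and says "These associations may be assessed using simple pairwise correlations and pairwise graphical relationship". It then allows more: "These relationships may also be described using a modeling approach, if appropriate". The direct ADA-SUVr pairing appears here, under permissive wording, and not in the interim sentence.

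Neither section gives dose or regimen as a covariate or stratum for these associations, or says whether regimens are pooled. The ADA-over-time mixed model in 4.2.7.3 does contain dose, but it answers a different question. SAP 4.2.6 plans descriptive exposure-response graphs that may be drawn by dose, exposure or time.

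**The concern.** Protocol 5.2 makes it an aim to "assess the relationship between PK, PD (amyloid removal), immunogenicity, and clinical safety" and lists an acceptable clinical impact of ADA among the conditions for further development. Protocol 5.1 reports that multiple dosing in the previous study was stopped because of ADA prevalence and rapid elimination. Whether ADA lowers exposure or blunts amyloid removal is therefore a question the sponsor will want these data to answer.

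The assigned regimen largely sets cumulative exposure and probably amyloid removal. It may also shift ADA: Protocol 7.2 suggests that higher and more frequent dosing could lower its incidence. A common cause of both variables confounds their raw correlation. The pooled figure could hide a real ADA effect on clearance or suggest one that is absent.

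**Working it through.** **Doses.** The protocol synopsis gives 13 Part B and 19 Part C doses. Number of doses = weeks/interval + 1: 24/2 + 1 = 13 and 72/4 + 1 = 19, so both are reproduced.

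**Total planned dose (mg/kg).** The range runs from "Cohort 1: 10 mg/kg IV single dose" to "Cohort 7: 20 mg/kg IV Q4W for up to 72 weeks".
- Full study, Cohorts 1 to 7: 10, 20, 40, 13×10 = 130, 13×20 = 260, 19×10 = 190, 19×20 = 380. Ratio 380/10 = 38.
- Scheduled through Day 169, with 24/4 + 1 = 7 doses in Part C: 10, 20, 40, 130, 260, 70, 140. Ratio 260/10 = 26.
- Cohorts 4 and 5 alone: 260/130 = 2.
- Dose per infusion: 40/10 = 4.

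**Group sizes** (Protocol 7.1.3 to 7.1.5): 3×6 + 4×9 = 54 active patients.

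**Model (assumed; the documents give no effect sizes).** Log titre A has SD 1 within regimen and is shifted by s SD in the multiple-dose cohorts. Log exposure = log dose − b·A + error, with error SD 0.3. I took b = 0, 0.2 and 0.3.

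**Within-regimen correlation** = −b/√(b² + 0.09).
- b = 0.2: −0.2/√0.13 = −0.55.
- b = 0.3: −0.3/√0.18 = −0.71 (simulated −0.70).

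**Pooled, equal titres (s = 0)** = −b/√(V + b² + 0.09). V, the variance of log total dose over the 54 patients, is 1.50 for the full study.
- b = 0.2: −0.2/√1.63 = −0.16.
- b = 0.3: −0.3/√1.68 = −0.23.

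**Pooled, no ADA effect (b = 0).** Mean log dose is 5.404 in the multiple-dose cohorts and 2.996 in the single-dose cohorts, a difference of 2.408. With 36/54 = 2/3 of patients on multiple dosing, the covariance per unit s is (2/3)(1/3)(2.408) = 0.535. The pooled r is 0.535s/√[(1 + 0.222s²)(1.50 + 0.09)].
- s = −1: −0.535/√(1.222×1.59) = −0.38.
- s = −0.5: −0.268/√(1.056×1.59) = −0.21.

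**Simulation, full study (mean pooled r, 3,000 trials per cell).**

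| s | b = 0 (within 0.00) | b = 0.2 (within −0.55) | b = 0.3 (within −0.70) |
|---|---|---|---|
| −1 | −0.39 | −0.52 | −0.57 |
| −0.5 | −0.21 | −0.35 | −0.41 |
| 0 | 0.00 | −0.15 | −0.23 |
| +0.5 | +0.20 | +0.05 | −0.03 |
| +1 | +0.39 | +0.23 | +0.14 |

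With b = 0, the pooled correlation is nominally significant (two-sided 5%) in 86% of trials at s = −1 and in 33% at s = −0.5.

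**Doses through Day 169, b = 0.2 and 0.3.** Pooled r is −0.18 and −0.26 with equal titres, 0.00 and −0.08 at s = +0.5, and +0.17 and +0.06 at s = +1.

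**Exposure proportional to per-infusion dose.** For b = 0.2 and 0.3 the pooled r stays between −0.26 and −0.59 for every s from −1 to +1. With b = 0 it is at most 0.13 in absolute value.

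**Smallest interim.** The trigger guarantees 4 + 4 = 8 active patients in Cohorts 4 and 5. At n = 8, |r| must exceed 2.447/√(6 + 2.447²) = 0.71 for two-sided p < 0.05.

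**The case against.** The strongest reply is that the plan does not commit to a misleading analysis. Pooling is an inference. The interim also gives ADA and imaging summaries by dose group, both sections leave room for modelling, and the analyses are exploratory (SAP 4.2.5). PK methods are in a separate plan (SAP 4.2.4.1), not available here, which may already relate ADA to clearance. All of this is fair and limits the seriousness. But the modelling options name no covariate, and the only method that SAP 4.2.7.3 and 4.3 specify has no regimen term.

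A second reply is that the size depends on the exposure measure. SAP 4.2.7.3 says only that PK estimates of exposure will be used, and SAP 4.2.5.3 allows an alternative to AUC. Proportionality to dose is also doubtful, since Protocol 9.3 says that "the exposure at 10 mg/kg did not appear to be proportional with the exposures seen at lower doses". This stands: the larger distortions belong to cumulative exposure.

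A reader might infer that the ADA effect will vanish or reverse. The documents do not support that. It needs higher titres under multiple dosing, and Protocol 7.2 hopes for the opposite. In that opposite case the sign of a true effect is kept, but pooling can create an association where none exists.

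A reader might also apply the 38-fold range to the interim, or enter placebo patients at zero exposure. The first is a full-study ceiling, because Protocol 7.1.5 lets Part C patients move to placebo infusions. The second conflicts with Protocol 10.2.3, which does not intend to assay drug concentration in placebo samples.

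**Conclusion.** The point holds in this form: the specified ADA associations lack a regimen term, and if they are pooled, regimen confounds them. With equal titres and cumulative exposure, a within-regimen correlation of −0.55 to −0.70 appears as about −0.15 to −0.23. Vanishing or reversal is possible only if multiple dosing raises titres enough. A spurious correlation of about −0.2 to −0.4 is possible if it lowers titres by 0.5 to 1 SD. With per-infusion exposure a true correlation is diluted without a change of sign.

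These sizes rest on the assumed b, s and residual SD and on dose-proportional exposure. No calculation was made for ADA against SUVr, where the argument is qualitative. It would be too strong to say that the plan tests these associations, since it sets no test or significance level for them. The primary SUVr comparison with placebo is unaffected.

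**What to change.** In SAP 4.2.7.3 and 4.3, for the ADA-exposure and ADA-SUVr associations only, and in LY3002813-treated patients:
- Use partial correlations adjusted for regimen, or regress log clearance (or log AUC) and SUVr change on log2 ADA titre with dosing regimen as a fixed effect. Dose-normalising AUC is not enough by itself, because clearance appeared to change with dose (Protocol 9.3).
- Mark regimen on the plots and label any pooled correlation descriptive.
- At the interim, where as few as 8 patients in Cohorts 4 and 5 are guaranteed, regimen-marked plots and descriptive regimen-adjusted estimates are enough.

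Leave the exposure-SUVr and exposure-safety analyses free to use between-dose variation, which is what they are meant to exploit. Cross-refer to the PK analysis plan if it already models ADA on clearance.

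The cost is SAP wording, with no new samples and, under SAP 4.2.5, no protocol amendment for changes to these exploratory analyses. At the final analysis, up to six degrees of freedom go to regimen among about 54 active patients.

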#### **4.4. Clinical Trial Registry Analysis Plan and DSUR**

Additional analyses will be performed for the purpose of fulfilling the Clinical Trial Registry (CTR) requirements.

Analyses provided for the CTR requirements include the following:

- Summary of AEs, provided as a dataset which will be converted to an XML file. Both SAEs and 'Other' AEs will be summarized: by treatment group, by MedDRA PT.
- An AE is considered 'Serious' whether or not it is a treatment emergent adverse event (TEAE).
- An AE is considered in the 'Other' category if it is both a TEAE and is not serious. For each SAE and 'Other' AE, for each term and treatment group, the following will be provided:
  - the number of participants at risk of an event
  - the number of participants who experienced each event term
  - the number of events experienced.
- Consistent with [www.ClinicalTrials.gov](http://www.ClinicalTrials.gov) requirements, 'Other' AEs that occur in fewer than 5% of patients/subjects in every treatment group may not be included if a 5% threshold is chosen (5% is the minimum threshold).

- Adverse event reporting is consistent with other document disclosures for example, the CSR, manuscripts, and so forth. AE reporting is consistent with other document disclosures for example, the CSR, manuscripts, and so forth.

The following reports will be included the DSUR:

- [1] Estimated cumulative subject exposure,
- [2] Cumulative exposure to investigational drug by demographic characteristics for ongoing unblinded clinical trials and completed clinical trials,
- [3] Exposure information for ongoing clinical trials and clinical trials that completed during the reporting period
- [4] Listing of subjects who died during the DSUR period,
- [5] Discontinuations due to an AE during the DSUR Period.

## 5. Unblinding Plan

Unblinding is described in the I5T-MC-AACD protocol under Attachment 4.

